6.8.3 Prohibited concomitant therapy

The following drugs are not permitted during the screening period and the 24-week randomized open-label treatment period:

- Any glucose-lowering agents other than the study interventions, authorized background antidiabetic therapy (metformin ± SGLT-2 inhibitor) and rescue therapy, if necessary.
- Note: Short time use (≤ 14 days) of short/rapid-acting insulin due to acute illness or surgery (eg, infectious disease) is allowed.
- Systemic glucocorticoids for more than 14 days (topical or inhaled applications are allowed).
- Body weight loss drugs which is defined as prescription medications with indication to treat overweight or obesity.
- Using any study interventional drugs other than those specified in this protocol.

After the last administration of study interventions during the study period, any antidiabetic treatments are permitted, as deemed necessary by the Investigator.

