2 ANALYSIS POPULATIONS

The following populations for analyses are defined.

Table 3 - Populations for analyses

Population	Description
Screened	All participants who signed the ICF.
Intent-to-treat (ITT)	All randomized participants. Participants will be analyzed according to the intervention allocated by randomization.
Per-protocol (PP)	All participants from ITT population who have completed 24 weeks of randomized treatment and did not start any rescue therapy before end of the 24-week randomized treatment period and have no major or critical protocol deviation that can potentially affect efficacy analysis. The protocol deviations for PP exclusion are defined in Section 5.7 and will be confirmed and finalized for each patient prior to the database lock. Participants will be analyzed according to the intervention allocated by randomization.
Safety	All randomized participants who have taken at least 1 dose of study intervention, regardless of the amount of treatment administered. Participants will be analyzed according to the intervention they actually received.

Participants exposed to study intervention before or without being randomized will not be considered randomized and will not be included in any analysis population. The safety experience of these participants will be reported separately.

Randomized participants for whom it is unclear whether they took the study intervention will be considered as exposed and will be included in the safety/population as randomized.

For any participant randomized more than once, only the data associated with the first randomization (except if the first randomization is done by error) will be used in any analysis population. The safety experience associated with any later randomization will be reported separately.

For participants receiving more than one study intervention during the study, the intervention group for as-treated analyses will be the intervention group as randomized if the participant received at least one administration as randomized.

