Unscheduled visit measurements of laboratory data and vital signs will be used for computation of baseline, the last on-treatment value, analysis according to PCSAs, and the shift summaries for safety. They will also be included in the by-visit summaries if they are re-allocated to scheduled visits.

5.5 APPENDIX 5 DEFINITION AND MEDICAL ALGORITHM FOR “RESCUED PARTICIPANTS” / RESCUE MEDICATION USE

Participants who meet one of the following conditions will be considered as “rescued”:

- In the eCRF page “Medications”, if there is any medication with “Rescue Therapy” ticked for “Reason for Treatment”.
- In the eCRF page “Medications”, if there is no medication with “Rescue Therapy” ticked for “Reason for Treatment” and the participant meets any of the criteria in medical algorithm for rescued participants, defined as below.

Medical algorithm for rescued participants

- Short/rapid-acting insulin is given for > 10 days continuously, or ≤ 10 days continuously if it occurs within 2 weeks prior to the last HbA1c measurement.
- New OAD is taken in addition to metformin+/- SGLT-2i (identified from eCRF page “Medications”) > 10 days continuously, or ≤ 10 days continuously if it occurs within 2 weeks prior to the last HbA1c measurement.
- The dose of background therapy is increased for > 10 days continuously, or ≤ 10 days continuously if it occurs within 2 weeks prior to the last HbA1c measurement.

Nevertheless, the participants must not be considered rescued if:

- The date of anti-diabetic initiation is on or after the date of last IMP injection.
- The date of anti-diabetic initiation is before Week 12.
- The anti-diabetic medication was taken due to IMP unavailability during COVID-19 pandemic.

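### The SAP's rescue algorithm has no exception for short-acting insulin that the protocol permits for acute illness or surgery, so some permitted use from Week 12 onward is counted as rescue

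*SAP*

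**What the plan says.** **Permission.** Protocol 6.8.3 prohibits glucose-lowering agents other than the study drugs, the background therapy and rescue therapy, and then adds a note: "Short time use (≤ 14 days) of short/rapid-acting insulin due to acute illness or surgery (eg, infectious disease) is allowed". The note stands apart from the mention of rescue.

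**Rescue in the protocol.** Under Protocol 6.8.4, rescue starts from an HbA1c above 8% at Week 12 or later. The investigator first looks for another explanation, including intercurrent disease. If there is one, the step is corrective action and a retest. Rescue can be considered if HbA1c stays above the threshold or no explanation is found.

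**Rescue in the SAP.** SAP 5.5 counts a participant as rescued if the Rescue Therapy box is ticked for a medication. It also does so "if there is no medication with “Rescue Therapy” ticked for “Reason for Treatment” and the participant meets any of the criteria" of a medical algorithm. The insulin criterion has two limbs. The first is a length of use: "Short/rapid-acting insulin is given for > 10 days continuously". The second catches shorter courses by their timing: "or ≤ 10 days continuously if it occurs within 2 weeks prior to the last HbA1c measurement".

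**Exceptions.** A participant is not rescued in three situations. One is a late start: "The date of anti-diabetic initiation is on or after the date of last IMP injection". Another is an early start: "The date of anti-diabetic initiation is before Week 12". The third is use of the drug because IMP was unavailable during the COVID-19 pandemic.

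**Use of the flag.** The per-protocol set in SAP 2 requires that a participant "did not start any rescue therapy before end of the 24-week randomized treatment period". SAP 3.2.4 and 3.3.1.3 set values after rescue to missing under the hypothetical strategy. SAP 3.3.2 analyses the percentage of participants requiring rescue.

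**The concern.** The algorithm is a back-up that runs when nobody recorded the drug as rescue. It does not look at why the insulin was given. A site that follows Protocol 6.8.3 during an infection or an operation, and correctly leaves the Rescue Therapy box unticked, can therefore have its participant reclassified as rescued.

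Three results are exposed. The rescue percentage would include people who never met the protocol's HbA1c trigger. The per-protocol set, which supports the non-inferiority conclusion, would lose people who did nothing the protocol forbids. The hypothetical estimands would discard HbA1c and body weight values observed after a permitted course.

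SAP 1 reports no major changes to the protocol's analyses, and the version history lists only the insulin-dose estimand. Nothing presents the algorithm as a deliberate redefinition of rescue.

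**Working it through.** The plan gives no figure for illness-related insulin use, so there is none to reproduce; its sample size does not depend on this point. The check applies the SAP rule to every course length that the protocol permits.

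**Inputs**
- Permitted length for acute illness or surgery: 1 to 14 days (Protocol 6.8.3).
- Limb 1: more than 10 continuous days. Limb 2: 10 days or fewer, within 2 weeks before the last HbA1c (SAP 5.5).
- Exceptions: start before Week 12; start on or after the last IMP injection; IMP unavailable because of COVID-19 (SAP 5.5).

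**Rule.** Flagged = (start at Week 12 or later) and (start before the last IMP injection) and (not COVID-19 supply) and (length > 10 days, or within 2 weeks before the last HbA1c).

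**Result for permitted illness or surgery insulin, no box ticked**

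| Start of insulin | Position relative to last HbA1c | Permitted lengths flagged as rescue |
|---|---|---|
| Before Week 12 | any | none |
| On or after last IMP injection | any | none |
| Week 12 or later, before last IMP injection | not within 2 weeks before it | 11, 12, 13 and 14 days |
| Week 12 or later, before last IMP injection | within 2 weeks before it | every length from 1 to 14 days |

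**Does another rule undo the flag?** No exception mentions illness or surgery, and the algorithm applies precisely when no rescue reason is recorded.

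**Effect by analysis**
1. *Percentage requiring rescue (SAP 3.3.2).* Each flagged participant counts as an event.
2. *Per-protocol set (SAP 2).* A flagged participant fails the no-rescue condition. Permitted insulin is not the prohibited-therapy deviation in SAP 5.7, so without the flag this use would not exclude anyone.
3. *Hypothetical estimands (SAP 3.2.4, 3.3.1.3).* HbA1c is scheduled at Weeks 12, 18 and 24 in this period. A course started between the Week 12 and Week 18 visits removes two scheduled values; one started between the Week 18 and Week 24 visits removes Week 24. Body weight is lost in the same way. Under limb 2 the HbA1c lost is the participant's last, normally Week 24.
4. *Primary estimands of the primary endpoint and of 2a to 2e (SAP 3.2.2, 3.3.1.2).* All use treatment policy for rescue, so the flag removes nothing. SAP 3.5 confines gate-keeping to these analyses.

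**The case against.** The strongest defence is that the two numbers do different jobs. The protocol's 14 days limits what may be prescribed. The SAP's 10 days decides when added treatment counts as an intercurrent event. Permitted treatment can be an intercurrent event; rescue is itself permitted by Protocol 6.8.3. Because Protocol 6.8.4 recommends a rapid- or short-acting insulin for rescue, a back-up that catches unticked rescue is sensible. Limb 2 appears meant to protect the last HbA1c from recent extra insulin.

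Much of this stands. A reader might infer that the documents contradict each other on one and the same quantity. They do not: one is a permission and the other an analysis flag. The fault is that the flag ignores the reason for use. For the hypothetical estimands the defence has real weight, since setting values aside after added insulin is what that strategy does, and keeping a Week 24 value taken just after such insulin could also distort the estimate.

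The defence does not reach the other two uses. An endpoint described as requiring rescue should not count insulin given for an infection, when Protocol 6.8.4 treats intercurrent disease as a reason to correct and retest. Nor does protecting the HbA1c reading explain why a compliant participant leaves the per-protocol set after a course of a day or two: Protocol 3.1 describes HbA1c as reflecting the previous 120 days.

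**Conclusion.** The gap is real and follows from the wording alone: SAP 5.5 has no exception for insulin that Protocol 6.8.3 permits for acute illness or surgery. It is limited to insulin started at Week 12 or later and before the last IMP injection, and to the courses in the table.

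Three stronger readings are not supported:
- *That every protocol-compliant user of such insulin is classed as rescued.* Earlier starts, and starts on or after the last IMP injection, are exempt. Courses of 10 days or fewer away from the last HbA1c are not flagged.
- *That the non-inferiority or superiority tests are at risk.* The primary estimands use all values irrespective of rescue. What is exposed is supplementary analyses and one other secondary endpoint without multiplicity control.
- *That the distortion can be quantified.* The documents give neither the frequency of illness-related insulin nor a rescue rate. If 1% to 3% of participants were wrongly flagged and true rescue were 5%, the relative overstatement would be 1/5 = 20% to 3/5 = 60%. With true rescue at 10%, it would be 1/10 = 10% to 3/10 = 30%. All these rates are assumptions, and they only show how far the answer depends on them. Losses from the per-protocol set cannot be stated either, as some flagged participants may already be excluded for other reasons.

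The point is worth settling before database lock, but it does not change the primary conclusion.

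**What to change.** Reconcile Protocol 6.8.3 and SAP 5.5 before database lock.

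- Add to the SAP 5.5 list of participants not considered rescued those whose insulin has a recorded reason of acute illness or surgery and falls within the protocol's allowance. Apply this at least to the rescue percentage and the per-protocol exclusion. Leave the flag in place for other short-acting insulin.
- The sponsor chooses the duration. If the 10-day limit is meant to apply to illness insulin as well, the SAP should say so and give the reason.
- If limb 2 is kept to protect the hypothetical estimands, state it as a separate rule for those analyses. Report participants flagged only by the algorithm apart from investigator-declared rescue.
- Confirm that the eCRF reason field identifies illness or surgery. Protocol 6.8 requires the reason and the dates for each medication, but SAP 5.5 names only the Rescue Therapy value of that field.

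The cost is a short addition to SAP 5.5 and a check of the eCRF options; no new data are needed if the field already identifies such use. The small downside is that some HbA1c values taken shortly after permitted insulin stay in the supplementary analyses.

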5.6 APPENDIX 6 CRITERIA FOR POTENTIALLY CLINICALLY SIGNIFICANT ABNORMALITIES

CRITERIA for POTENTIALLY CLINICALLY SIGNIFICANT ABNORMALITIES for phase 2/3 studies (oncology excepted)

Parameter	PCSA	Comments
Clinical Chemistry		
ALT	By distribution analysis : >3 ULN >5 ULN >10 ULN >20 ULN	Enzymes activities must be expressed in ULN, not in IU/L. Concept paper on DILI – FDA draft Guidance Oct 2007. Internal DILI WG Oct 2008. Categories are cumulative. First row is mandatory. Rows following one mentioning zero can be deleted.
AST	By distribution analysis : >3 ULN >5 ULN >10 ULN >20 ULN	Enzymes activities must be expressed in ULN, not in IU/L. Concept paper on DILI – FDA draft Guidance Oct 2007. Internal DILI WG Oct 2008. Categories are cumulative. First row is mandatory. Rows following one mentioning zero can be deleted.
Alkaline Phosphatase	>1.5 ULN	Enzymes activities must be expressed in ULN, not in IU/L. Concept paper on DILI – FDA draft Guidance Oct 2007. Internal DILI WG Oct 2008.

**CRITERIA for POTENTIALLY CLINICALLY SIGNIFICANT ABNORMALITIES
for phase 2/3 studies (oncology excepted)**

Parameter	PCSA	Comments
Total Bilirubin	>1.5 ULN >2 ULN	Must be expressed in ULN, not in μ mol/L or mg/L. Categories are cumulative. Concept paper on DILI – FDA draft Guidance Oct 2007. Internal DILI WG Oct 2008.
Conjugated Bilirubin	>35% Total Bilirubin and TBILI>1.5 ULN	Conjugated bilirubin dosed on a case-by-case basis.
ALT and Total Bilirubin	ALT>3 ULN and TBILI>2 ULN	Concept paper on DILI – FDA draft Guidance Oct 2007. Internal DILI WG Oct 2008. To be counted within a same treatment phase, whatever the interval between measurement.
CPK	>3 ULN >10 ULN	FDA Feb 2005. Am J Cardiol April 2006. Categories are cumulative. First row is mandatory. Rows following one mentioning zero can be deleted.
CLcr (mL/min) (Estimated creatinine clearance based on the Cokcroft-Gault equation)	<15 (end stage renal disease) ≥15 - <30 (severe decrease in GFR) ≥30 - < 60 (moderate decrease in GFR) ≥60 - <90 (mild decrease in GFR) ≥ 90 (normal GFR)	FDA draft Guidance 2010 Pharmacokinetics in patients with impaired renal function- study design, data analysis, and impact on dosing and labeling
eGFR (mL/min/1.73m ²) (Estimate of GFR based on an MDRD equation)	<15 (end stage renal disease) ≥15 - <30 (severe decrease in GFR) ≥30 - < 60 (moderate decrease in GFR) ≥60 - <90 (mild decrease in GFR) ≥ 90 (normal GFR)	FDA draft Guidance 2010 Pharmacokinetics in patients with impaired renal function- study design, data analysis, and impact on dosing and labeling
Creatinine	≥150 μ mol/L (Adults) ≥30% change from baseline ≥100% change from baseline	Benichou C., 1994.
Uric Acid		Harrison- Principles of internal Medicine 17 th Ed., 2008.
Hyperuricemia	>408 μ mol/L	
Hypouricemia	<120 μ mol/L	
Blood Urea Nitrogen	≥17 mmol/L	
Chloride	<80 mmol/L >115 mmol/L	
Sodium	≤129 mmol/L ≥160 mmol/L	

**CRITERIA for POTENTIALLY CLINICALLY SIGNIFICANT ABNORMALITIES
for phase 2/3 studies (oncology excepted)**

Parameter	PCSA	Comments
Potassium	<3 mmol/L ≥5.5 mmol/L	FDA Feb 2005.
Total Cholesterol	≥7.74 mmol/L	Threshold for therapeutic intervention.
Triglycerides	≥4.6 mmol/L	Threshold for therapeutic intervention.
Lipasemia	≥3 ULN	
Amylasemia	≥3 ULN	
Glucose		
Hypoglycaemia	≤3.9 mmol/L and <LLN	ADA May 2005.
Hyperglycaemia	≥11.1 mmol/L (unfasted); ≥7 mmol/L (fasted)	ADA Jan 2008.
HbA1c	>8%	
Albumin	≤25 g/L	
CRP	>2 ULN or >10 mg/L (if ULN not provided)	FDA Sept 2005.
Hematology		
WBC	<3.0 Giga/L (Non-Black); <2.0 Giga/L (Black) ≥16.0 Giga/L	Increase in WBC: not relevant. To be interpreted only if no differential count available.
Lymphocytes	>4.0 Giga/L	
Neutrophils	<1.5 Giga/L (Non-Black); <1.0 Giga/L (Black)	International Consensus meeting on drug-induced blood cytopenias, 1991. FDA criteria.
Monocytes	>0.7 Giga/L	
Basophils	>0.1 Giga/L	
Eosinophils	>0.5 Giga/L or >ULN (if ULN≥0.5 Giga/L)	Harrison- Principles of internal Medicine 17 th Ed., 2008.
Hemoglobin	≤115 g/L (Male); ≤95 g/L (Female) ≥185 g/L (Male); ≥165 g/L (Female) Decrease from Baseline ≥20 g/L	Criteria based upon decrease from baseline are more relevant than based on absolute value. Other categories for decrease from baseline can be used (≥30 g/L, ≥40 g/L, ≥50 g/L).
Hematocrit	≤0.37 v/v (Male) ; ≤0.32 v/v (Female) ≥0.55 v/v (Male) ; ≥0.5 v/v (Female)	
RBC	≥6 Tera/L	Unless specifically required for particular drug development, the analysis is redundant with that of Hb. Otherwise, consider FDA criteria.
Platelets	<100 Giga/L ≥700 Giga/L	International Consensus meeting on drug-induced blood cytopenias, 1991.

**CRITERIA for POTENTIALLY CLINICALLY SIGNIFICANT ABNORMALITIES
for phase 2/3 studies (oncology excepted)**

Parameter	PCSA	Comments
Urinalysis		
pH	≤4.6 ≥8	
Vital signs		
HR	≤50 bpm and decrease from baseline ≥20 bpm ≥120 bpm and increase from baseline ≥20 bpm	To be applied for all positions (including missing) except STANDING.
SBP	≤95 mmHg and decrease from baseline ≥20mmHg ≥160 mmHg and increase from baseline ≥20 mmHg	To be applied for all positions (including missing) except STANDING.
DBP	≤45 mmHg and decrease from baseline ≥10 mmHg ≥110 mmHg and increase from baseline ≥10 mmHg	To be applied for all positions (including missing) except STANDING.
Orthostatic Hypotension		
Orthostatic SDB	≤-20 mmHg	
Orthostatic DBP	≤-10 mmHg	
Weight	≥5% increase from baseline ≥5% decrease from baseline	FDA Feb 2007.
ECG		
HR	<50 bpm <50 bpm and decrease from baseline ≥20 bpm <40 bpm <40 bpm and decrease from baseline ≥20 bpm <30 bpm <30 bpm and decrease from baseline ≥20 bpm	Categories are cumulative
	>90 bpm >90 bpm and increase from baseline ≥20bpm >100 bpm >100 bpm and increase from baseline ≥20bpm >120 bpm >120 bpm and increase from baseline ≥20 bpm	Categories are cumulative

**CRITERIA for POTENTIALLY CLINICALLY SIGNIFICANT ABNORMALITIES
for phase 2/3 studies (oncology excepted)**

Parameter	PCSA	Comments
PR	>200 ms >200 ms and increase from baseline $\geq 25\%$ > 220 ms >220 ms and increase from baseline $\geq 25\%$ > 240 ms > 240 ms and increase from baseline $\geq 25\%$	Categories are cumulative
QRS	>110 ms >110 msec and increase from baseline $\geq 25\%$ >120 ms >120 ms and increase from baseline $\geq 25\%$	Categories are cumulative
QT	>500 ms	
QTc	Absolute values (ms) >450 ms >480 ms >500 ms Increase from baseline Increase from baseline]30-60] ms Increase from baseline >60 ms	To be applied to any kind of QT correction formula. Absolute values categories are cumulative QTc >480 ms and $\Delta QTc > 60$ ms are the 2 PCSA categories to be identified in individual subjects/patients listings.

5.7 APPENDIX 7 PRE-DEFINED PROTOCOL DEVIATIONS AND CATEGORIZATION

Category for Protocol Deviation* (severity) (DVCATINI)	Protocol Deviation Coded Term* (DVDECOD)	Deviation Number* (DVSPID)	Protocol Deviation Term* (DVTERM)	Inclusion/Exclusion criterion number (IETESTCD)	Inclusion/Exclusion from PPS
CRITICAL	Informed consent procedures	0101	Study Informed consent/ Assent form never obtained for the study and personal data collected or intervention(s) performed	N/A	Exclude
CRITICAL	Informed consent procedures	0104	Study Informed consent/Assent form not obtained for an amendment requiring a re-consent	N/A	Exclude
MAJOR	Inclusion/Exclusion criteria	0201	Participant must be at least 18 of age inclusive, at the time of signing the informed consent.	I01	Exclude
MAJOR	Inclusion/Exclusion criteria	0202	Participants who are diagnosed with T2DM for at least 1 year before the screening visit	I02	Exclude if less than 11 months; Include otherwise
MAJOR	Inclusion/Exclusion criteria	0203	Treated for \geq 3 months prior to the visit 1 with a stable dose of metformin (\geq 1000 mg/day or the MTD) alone or plus a second oral antidiabetic treatment	I03	Include if \geq 90 days; Exclude otherwise
MAJOR	Inclusion/Exclusion criteria	0204	HbA1c at visit 1: 7.5% to 11%, if treated with metformin +/- SGLT-2 inhibitor, or 7.0% to 10%, if treated with metformin + a 2nd OAD other than SGLT-2 inhibitor.	I04	Exclude
MAJOR	Inclusion/Exclusion criteria	0206	Body mass index (BMI) <40 kg/m ² at screening	I06	Exclude case by case during PD review before DBL
MAJOR	Inclusion/Exclusion criteria	0235	Previous treatment with insulin (except for short-term treatment \leq 14 days due to intercurrent illness at the discretion of the Investigator) within 1 year prior to screening.	E05	Exclude

Category for Protocol Deviation* (severity) (DVCATINI)	Protocol Deviation Coded Term* (DVDECOD)	Deviation Number* (DVSPID)	Protocol Deviation Term* (DVTERM)	Inclusion/Exclusion criterion number (IETESTCD)	Inclusion/Exclusion from PPS
MAJOR	Inclusion/Exclusion criteria	0236	Use of oral or injectable glucose-lowering agents other than those stated in the inclusion criteria within 3 months prior to screening.	E06	Exclude
MAJOR	Inclusion/Exclusion criteria	0237	Use of systemic glucocorticoids (excluding topical application or inhaled forms) for 1 week or more within 3 months prior to screening.	E07	Exclude case by case during PD review before DBL
MAJOR	Inclusion/Exclusion criteria	0238	Use of weight loss drugs within 3 months prior to screening.	E08	Exclude
MAJOR	Inclusion/Exclusion criteria	0240	Use of any investigational drug other than specified in this protocol within 1 month or 5 half-lives, whichever is longer, prior to screening.	E10	Exclude
MAJOR	Concomitant Medications/ Therapy	0301	NIMP not administered	N/A	Exclude case by case during PD review before DBL
MAJOR	Concomitant Medications/ Therapy	0303	Protocol prohibited therapy/medication/vaccine/ administered	N/A	Exclude
MAJOR	IMP Management	0501	IMP not administered	N/A	Exclude based on automatic PD
MAJOR	Randomization procedure	0605	IMP kit number actually dispensed to the participant is different from the IMP kit number allocated	N/A	Exclude if IMP treatment number doesn't correspond to the IMP allocated per randomization process (ie, participant switched from treatment group).
